# 1.3.1.4 NK Cells Apoptosis

Aside from T cells, the immunotoxin-antibody combination WT1-RTA also targets NK cells (CD3-/CD7+). In the Phase I/II clinical study using T-Guard, NK cells demonstrated the same depletion pattern as T cells, an early and quick depletion during the seven-day treatment period, followed by a rapid repopulation of the NK cell compartment (Groth, van Groningenet al. 2018). The NK cell depletion is thought to contribute to controlling established aGVHD disease, as NK cells may aggravate the severity of aGVHD through cytokine production, e.g. Interferon (IFN)-gamma (Gill, Olson et al. 2009).

# 1.3.2 Clinical data

# 1.3.2.1 Clinical Experience with T-Guard in Patients with SR-aGVHD

T-Guard has been evaluated in two clinical trials: as third-line therapy in an investigator-initiated dose escalation-study in seven patients suffering from SR-aGVHD (van Oosterhout, van Emst et al. 2000, van Oosterhout, van Emst et al. 2001) and as second-line therapy in a Phase I/II study in 20 patients with SR-aGVHD (Groth, van Groningen et al. 2017). Results from these studies are summarized below.

## **1.3.2.2** T-Guard Dose Escalation Study as Third Line for SR-aGVHD Patients

The main purpose of the investigator-initiated dose escalation study was to test the safety and pharmacokinetics (PK) of T-Guard. A total of seven male Caucasian patients, with a median age of 47 with SR-aGVHD that had failed second line therapy were included. Three of these patients (43%) had aGVHD Grade IV, 3 patients (43%) Grade III and 1 patient Grade II (14%). Six patients (86%) had visceral organ involvement, including four patients (57%) with liver involvement and two patients (29%) with GI involvement. One patient (14%) had grade IV aGVHD of the skin. Before T-Guard treatment, all patients received an initial course of steroids at 1-2mg/kg/day for at least 7 days, followed by 1 gram of methylprednisolone equivalent per day or at least 3 days to treat SR-aGVHD. The first two patients started with T-Guard 2mg/m^2 infused every 48 hours x 2 doses, followed by 4mg/m^2 every 48 hours x 2 doses. There were no toxicities associated with the T-Guard treatment, and therefore the next five patients were scheduled to receive 4mg/m^2 every 48 hours x 4 doses.

The infusions were well tolerated, and biologic and clinical responses, as further described below, were achieved. Given the activity and tolerance of the 4mg/m^2 every 48 hours x 4 doses schema, no further dose escalation was completed. The study team was concerned for capillary leak syndrome (CLS), which is a known complication of ricin-based immunotoxins. However, none of the patients had any severe toxic side effects (grade 3 or higher Common Terminology Criteria for Adverse Events (CTCAE) 4.3) associated with RTA-based immunotoxins, like severe CLS and rhabdomyolysis. Regarding Treatment Emerging Adverse Events (TEAE), the most frequent reported adverse events (AE) were: pyrexia (43%) and headache (29%) followed by pain, edema, aphasia, dizziness, epilepsia, diarrhea, hemorrhoids, paralytic ileus and protein losing gastroenteropathy (all 14%).

PK analysis showed that the 4mg/m^2 every 48 hours x 4 doses schedule resulted in T-Guard in vivo serum peak concentration (Cmax) of around 1.5  $\mu$ g/ml (~10^-8M). On the basis of in vitro experiments, the Cmax attained results in a 60-80% occupation of the target antigens CD3 and CD7 and corresponds with the optimal in vitro concentration for a specific elimination of antigen-positive target cells (Figure 1-3).

Four patients were evaluated for biologic response with flow cytometric quantitation of NK and T cell levels. All of these patients showed a rapid and profound reduction in circulating T cells and NK cells, with additional doses leading to further reduction (less than 10-20%) of initial levels of circulating NK and T cells. With this prompt and marked decline in NK and T cells there was clinical improvement in GVHD, with four of the seven patients having clinically meaningful and rapid reduction in their GVHD. Five out of 7 patients (71%) responded. One patient (14%) was in complete remission, 4 patients (57%) had a PR. To date 6 patients died, two during the first eight days of treatment with T-Guard. All patient deaths were related to multisystem organ failure and opportunistic infections.

Since the dose level of T-Guard at 4 mg/m^2 x 4 doses generated biologically relevant serum concentrations ( $C_{max}$  of 1.36 ± 0.27 µg/mL) which resulted in clear biological and clinical responses without inducing severe acute toxicities, the dosage was not further increased to prevent potentially dangerous dose limiting toxicities (DLTs).

# 1.3.2.3 Single-arm, Phase 1/2 Clinical trial in second line SR-aGVHD Patients

Following the promising results of T-Guard for the indication SR-aGVHD in the investigatorinitiated dose escalation study, a Phase 1/2 study XEN/TG-001 was conducted (Groth, van Groningen et al. 2018). The study was designed to evaluate the safety and efficacy of T- Guard in treating SR-aGVHD patients who were refractory to first-line therapy. Regarding the IMP (T-Guard), a switch was made to non-glycosylated bacterial produced recombinant RTA. In total 20 patients were treated with T-Guard with a dose of 4 mg/m^2 every other day x 4 doses. All patients had SR grade II to IV aGVHD. Seventeen of these patients (85%) had severe SR-aGVHD, and all 20 patients had visceral involvement; 18 GI (90%) and 5 liver (25%) involvement. Sixteen patients (80%) had 2 or more organs involved. A validated two biomarker algorithm classified the majority of patients (11/20) as high-risk.

The Day 28 ORR (primary endpoint), defined as having a CR or PR without the need for initiation of other treatments due to insufficient response, was 60%. Day 28 CR was 50% and PR 10%. The Day 180 OS was 60%. The outcomes achieved were very favorable compared with the historical standard of care (SoC) data at the participating centers (Day 28 CR less than 20% and Day 180 OS 29%).

#### 1.3.2.4 Safety

The most common side-effects described for RTA-based immunotoxins are vascular leakage and myalgia, the latter being often associated with an increase in serum creatine kinase (CK). Moreover, the systemic administration of anti-CD3 antibodies may result in the activation of Tcells leading to CRS. In both trials T-Guard was overall well-tolerated. Mild infusion related reactions, such as mild chills, were documented. However, no acute toxicity reactions seen were greater than Grade 1. The most commonly reported AEs considered to be related to T- Guard administration were hypoalbuminemia and thrombocytopenia.

The potentially drug-associated side effects occurring in more than one patient consisted of (further) decrease in platelet count (thrombocytopenia), hypoalbuminemia and thrombotic microangiopathy. Regarding thrombocytopenia and hypoalbuminemia, the patients in the study already had a low platelet count and albumin level due to aGVHD and medication. Nevertheless, in several patients, a further decrease was observed during the treatment period. According to the Principal Investigators, thrombocytopenia and hypoalbuminemia were well-manageable. TEAEs from the overall study are outlined in Table 1-1 from the Phase I/II Trial.

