# 3.4.2.9 Incidence of Toxicities

All grade 3-5 toxicities according to CTCAE v5 occurring from the initiation of T-Guard treatment to 28 days post last dose will be described.

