#### Prior to Enrollment

The following pre-enrollment assessments must be completed prior to enrolling the patient in Advantage eClinical and within the designated timeframe listed below.

1. Complete acute GVHD staging and grading information including assessments of rash, diarrhea, nausea/vomiting, and bilirubin, within 24 hours prior to enrollment. Biopsy results of involved tissue, if performed as SoC, should also be reported.

- 2. Albumin, platelet count, and CK level within 24 hours prior to enrollment
- 3. Complete blood count (CBC) with differential within 24 hours prior to enrollment
- 4. Pregnancy test (urine or serum) for females of child-bearing potential within 30 days prior to enrollment

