#### At Each Infusion of T-Guard Therapy

- 1. Complete acute GVHD staging and grading information including assessments of rash, diarrhea, nausea/vomiting, and bilirubin
- 2. Vital signs (temperature, pulse, respiratory rate, blood pressure) just before starting the infusion, 15 minutes after the start of the infusion, 30 minutes after the start of the infusion, then every 30 minutes during the infusion, and at 1-hour post-infusion\*. Deviation of +/- 5 minutes may occur for all vital sign collection timepoints.
- 3. Albumin and platelet count prior to each dose of T-Guard
- 4. CBC with differential
- Peripheral blood\* for immunophenotyping studies pre-infusion and at 4 hours after the start of infusion. Pre-infusion samples should be drawn prior to T-Guard administration and a window of +/- 15 minutes is allowed for the sample drawn 4 hours after the start of infusion.
- 6. Peripheral blood\* for PK at the following timepoints
  - a. 1st infusion: pre-infusion, and at 4, 5, 6, 8, and 24 hours after start of infusion
  - b. 2nd infusion: pre-infusion, and at 4, 6, and 24 hours after start of infusion
  - c. 3rd infusion: pre-infusion, and at 4, 6, and 24 hours after start of infusion
  - d. 4th infusion: pre-infusion, and at 4, 6, 24, and 48 hours after start of infusion

Pre-infusion samples should be drawn prior to T-Guard administration. A window of +/- 15 minutes for samples drawn at 4,5, or 6 hours after the start of infusion, and a window of +/-30

minutes for the sample drawn 8 hours after the start of infusion is allowed. A window of +/- 2 hours for samples drawn 24 or 48 hours after the start of infusion is also allowed. Every effort should be made to collect PK samples at all timepoints, however, the treatment schedule should not be altered to accommodate PK sampling. For example, if T-Guard administration is scheduled for a weekend and PK sampling is not possible then administration should occur on schedule. In the event weekend PK sample collection is missed, collection of PK samples should be resumed at the next T-Guard infusion. Please refer to Section 4.5 for more information regarding infusion delays.

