#### Post-Initiation of T-Guard Therapy

The following assessments and observations must be completed at the timepoints designated below.

- 1. Complete acute GVHD staging and grading information including assessments of rash, diarrhea, nausea/vomiting, and bilirubin at Days 7, 14, 21, 28, 35, 42, 49, 56, 70, 90, and 180
- 2. Albumin and platelet count at Days 28, 56, 90, and 180
- 3. CBC with differential at Days 28, 56, 90, and 180 (must be collected at the same time as the 30mL peripheral blood for alloreactive T-cell sample on Days 28 and 180)
- 4. Karnofsky or Lansky performance status at Days 28, 56, 90, and 180
- Peripheral blood for EBV and CMV viral load at Days 28 and 180 with monitoring of EBV and CMV continuing per institutional practice post Day 28 through 180 days post initiation of T-Guard
- 6. Peripheral blood\* for EBV, CMV-specific and alloreactive T-cells at Days 28 and 180
- 7. Patient reported outcomes at Days 28, 56 and 180 post initiation of T-Guard
- 8. cGVHD evaluation (if present) Day 28, 56, 90, and 180
- 9. Peripheral blood\* for ADA testing at Days 7, 14, 28, 90, and 180
- 10. Peripheral blood\* for immunophenotyping studies at Days 14, 28, 56, and 180
- 11. Peripheral blood\* and urine sample\* at Days 7, 14, and 28 for GVHD biomarker testing
- 12. Recording of all systemic immune suppressive therapy (as appropriate: tacrolimus, cyclosporine, etc.), as well as topical agents, and all anti-infectives used for prophylaxis or treatment at Days 7, 14, 21, 28, 35, 42, 49, 56, 70, 90, and 180
- 13. Recording of toxicities on Days 56, 70, 90, and 180
- 14. Recording of AE/SAEs as described in Section 4.4 Adverse Event Reporting
- 15. Recording of infections through Day 180
- 16. Recording of primary disease relapse through Day 180

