# 4.4.4 Required Adverse Event Reporting

Any unanticipated SAEs from time of enrollment through the study defined follow up are required to be reported following the BMT CTN Administrative MOP Chapter 6. Additionally, any grade 4 anticipated event not collected on the calendar-driven toxicity or specified event- driven form must **also** be reported through the expedited AE reporting system in Advantage eClinical. Chapter 6 of the BMT CTN MOP defines reporting based on the terms Unexpected and Expected; however, for this study, the reporting will be based on the terms Unanticipated and Anticipated All adverse events, including SAEs, must be reported from the 1st dose of T- Guard through 30 days after the last dose. In addition, any SAEs occurring after that 30-day period, but assessed as related to the investigational product, must be reported. All SAEs are to be followed up until resolved, judged to be no longer clinically significant, or until they become chronic to the extent that they can be fully characterized.

Infections are collected separately in eClinical as this is a study endpoint; however, should an infection meet the SAE criteria the infection must also be reported following the SAE reporting criteria outlined above.

GVHD and underlying disease relapse events are also collected separately in eClinical because they are part of the endpoint analysis. Events of GVHD and underlying disease relapse are not to be reported as AEs/SAEs for this study.

The Sponsor has a list of events classified as Special Situations. These events are 1) medication error, 2) overdose and 3) pregnancy. These events must be reported following the reporting for SAEs.

SAEs that require reporting will be reported through an expedited AE reporting system via an EDC. All SAEs, as well as Special Situations, must be reported within 24 hours of knowledge of the event. Events entered in EDC will be reported using NCI's CTCAE Version 5.0. If there are network outages, a paper copy of the AE form must be completed and emailed to Emmes to initiate Sponsor review. Once the system is available, the event information must be entered into the system.

Anticipated AEs will be reported using NCI's CTCAE Version 5.0 at regular intervals as defined on the Form Submission Schedule, including calendar-driven eCRFs (e.g., Toxicity and GVHD) or event-driven eCRFs (e.g., Relapse/Progression, Infection, Secondary Graft Failure and Death).

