#### 5.4.11 Incidence of Toxicities

The frequency of Grade 3-5 toxicities per CTCAE version 5 occurring from the initiation of T-Guard treatment until 28 days post-last dose will be tabulated by organ system. The maximum severity of reported toxicities during that period will also be summarized.

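### Platelets and albumin are measured before every dose, but no planned analysis sets them against the patient's own starting value, so the Grade 3-5 table cannot show which abnormalities are new or worsened

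*Combined protocol and SAP*

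**What the plan says.** **Prior experience.** Section 1.3.2.4 identifies hypoalbuminemia and thrombocytopenia as the related events reported most often. It explains that Phase 1/2 patients were already low on both because of GVHD and medication, and continues: "Nevertheless, in several patients, a further decrease was observed during the treatment period".

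**Measurement.** Section 4.3.2 requires:
- "Albumin, platelet count, and CK level within 24 hours prior to enrollment"
- "Albumin and platelet count prior to each dose of T-Guard"
- "Albumin and platelet count at Days 28, 56, 90, and 180"

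**Analysis.** The endpoint in section 3.4.2.9 is "All grade 3-5 toxicities according to CTCAE v5 occurring from the initiation of T-Guard treatment to 28 days post last dose". Section 5.4.11 tabulates by organ system "The frequency of Grade 3-5 toxicities per CTCAE version 5 occurring from the initiation of T-Guard treatment until 28 days post-last dose" and adds: "The maximum severity of reported toxicities during that period will also be summarized". The baseline list in section 5.2.3 contains neither platelet count nor albumin.

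**Event reporting.** Section 4.4.4 states: "All adverse events, including SAEs, must be reported from the 1st dose of T- Guard through 30 days after the last dose". Section 4.4.1 narrows this for laboratory findings. An abnormal value counts as an adverse event only if it produces signs or symptoms, needs active intervention, interrupts or stops study drug, or is clinically significant in the investigator's opinion.

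**The concern.** In a single-arm trial, each patient's own value before the first dose is the only reference inside the trial for a laboratory change on treatment. These patients are expected to enter with low platelets and albumin. Section 2.4 sets no platelet minimum, and albumin excludes a patient only at or below 1 g/dL. A count of Grade 3-5 events therefore mixes two things: how ill the patients were at entry, and what happened after T-Guard started.

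At stake is what the final report can say about two of the leading related harms. The plan already uses change from baseline for anti-drug antibodies (5.4.13), cell subsets (5.5.7) and patient-reported outcomes (5.5.9), but not for these two values.

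**Working it through.** The plan gives no figure on this point to reproduce. The check compares what is measured with what is analyzed, and then works out which values fall inside the toxicity window.

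**Step 1. Does any Chapter 5 analysis use the values?**
- 5.2.2: the two sequential tests cover Day 30 mortality and Grade 4 or higher capillary leak syndrome (CLS).
- 5.2.3: neither value is in the baseline list.
- 5.4.11: Grade 3-5 counts and maximum severity, with no entry grade and no statement of how an abnormality present on Day 0 is counted.
- 5.4.12: neither value is among the named pharmacokinetic covariates.
- 5.4.13, 5.5.7, 5.5.9: change from baseline, but for other measures.

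None of them uses either value. Albumin is used operationally, for eligibility and for dose holds in section 2.5.5. That section has no platelet-specific hold, and its general clause covers non-hematologic toxicity only.

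**Step 2. What would the planned table show?** Take three hypothetical patients. One is at Grade 3 on Day 0 and stays there. One starts normal and falls to Grade 3. One starts normal and falls to Grade 2. If the first is recorded as an event, the first two look identical in the planned table and the third is absent. A shift table separates all three.

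**Step 3. Which values lie inside the 5.4.11 window?** The window closes 28 days after the last dose.
- Fourth dose on schedule: 6 + 28 = Day 34.
- Fourth dose at the 14-day limit (section 2.5.6): 14 + 28 = Day 42.
- Adverse event reporting closes 30 days after the last dose: 6 + 30 = Day 36, or 14 + 30 = Day 44. It covers the window but passes through the section 4.4.1 filter, so the scheduled values are the better source.
- After the last dose, scheduled values come at Day 28 and then Day 56. With the 3-day visit range, the earliest Day 56 visit is 56 − 3 = Day 53, outside the window. Day 28 is therefore the only scheduled post-treatment value inside it.
- Gap after an on-schedule fourth dose: 28 − 6 = 22 days with no scheduled value.

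The extracted Table 4.2 shows no platelet mark at Day 4. This may be an extraction fault, and the text of section 4.3.2 requires the count before each dose.

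**Step 4. What can Phase 1/2 say about size?**
- Table 1-1, all-cause events: hypoalbuminemia 8/20 = 40%, thrombocytopenia 6/20 = 30%.
- Table 1-2, potentially related thrombocytopenia: 1, 3 and 5 patients at Grades 2, 3 and 4. The footnote says these are patients, and nothing confines a patient to one grade. Distinct patients therefore number from 5 (full overlap) to 1 + 3 + 5 = 9 (none).
- Table 1-2, potentially related hypoalbuminemia: 1 patient at Grade 2 and 1 at Grade 3.
- Section 1.3.3 reports 7 mild and 1 moderate potentially related CLS cases, 8/20 in total. Table 1-2 shows only one CLS entry, at Grade 2, so it appears to omit Grade 1.
- Table 1-2 uses CTCAE v4.0 (CLS was graded on a separate scale); section 5.4.11 uses v5.

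These counts show that such events were common. They do not give the share that was pre-existing or the share that stayed below Grade 3.

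**The case against.** The strongest reply is that nothing is lost. The values are collected, so a shift table could be produced later. Section 5.4.11 covers only events occurring from the start of treatment, and under section 4.4.3 investigators weigh coexisting disease and medication when judging relationship. Section 5.2.2 provides regular toxicity monitoring and full board reviews after 10 and 30 evaluable participants. CLS, at 8/20 potentially related cases, was at least as frequent by count and has its own monitoring rule. The benefit of a fix is also limited by the 22-day gap, transfusion and the lack of controls.

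Much of this stands. A reader might infer that the trial could never tell a new abnormality from an old one. The documents do not support that: the separation is unplanned, not impossible. Nor should the two harms be called more frequent than CLS, or every Phase 1/2 patient be said to have fallen further; the text says several did.

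What remains is that an analysis added later would fix its baseline, window and worst-value rule after results are known. Investigator judgment and board review do not replace a summary against the entry value, and maximum severity without entry grade does not show change.

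**Conclusion.** The point holds as a gap in the planned safety description. The two values are measured repeatedly, several patients in the earlier study are reported to have fallen further, and no planned analysis uses the values. The Grade 3-5 table is not planned to separate new or worsened abnormalities from those present on Day 0, and it leaves out falls that stay below Grade 3.

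Its size cannot be given in patients. A reader might be tempted to take shares from Table 1-2, such as 8 of 9 thrombocytopenia entries at Grade 3-4 or 1 of 2 albumin entries below Grade 3, and project them to 47 patients. The overlap between grades, the apparent omission of Grade 1 and the different CTCAE version rule that out. Nor do Tables 1-1 and 1-2 contradict each other on thrombocytopenia: 6 patients lies within the possible 5 to 9.

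The conclusion assumes that Chapter 5 is the full analysis plan and that the expected low starting values carry over to this trial. Patient protection is not in question, given the albumin exclusion and hold and the CLS rule. The primary endpoint and error rates do not depend on it. This is a change the sponsor should make, at modest benefit and little cost.

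**What to change.** In section 5.2.3, add baseline platelet count and albumin.

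In section 5.4.11, for these two values, add:
1. A CTCAE v5 grade shift table from the Day 0 pre-dose value (if missing, the last value before the first infusion) to the worst recorded value within 28 days after the last dose.
2. Median and quartiles of change from Day 0 to each later pre-dose value, to the lowest recorded value and to Day 28.
3. A split of Grade 3-5 platelet and albumin events into new or worsened versus present on Day 0.

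Use the scheduled laboratory values as the source, placed by draw date, and state four limits:
- No value is scheduled between the fourth dose and Day 28.
- Platelet transfusion, allowed as supportive care in section 2.5.8.4, can mask falls.
- Section 2.5.5 lets dosing rest on an albumin up to 48 hours old.
- There is no control arm, so a shift describes change and does not establish cause.

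The cost is a few descriptive tables from values already required. No samples, visits, sample size or stopping rules change.
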